11.1.1.2 Sensitivity analysis

Sensitivity analyses will be performed to determine the robustness of the analysis results. In the individual sensitivity analyses, treatment effects will be estimated as with primary analysis. However, this is not presented in graphs.

Multiple imputation (MI) will be performed 100 times.

1) MI - MMRM

Multiple imputed data will be generated in the procedures shown below. Each imputation data will be analyzed using the same MMRM model as that for the primary analysis, and the results of the analyses will be combined. Imputation will be performed for all available data obtained at each time point between the baseline and Week 4 of the double-blind period.

- (1) Non-monotone missing data will be imputed with a Markov Chain Monte Carlo (MCMC) method.
- (2) Monotone missing data will be imputed with an imputation formula generated using a regression model developed based on the data from all the groups.

2) Placebo MI - MMRM

Multiple imputed data will be generated in the procedures shown below. Each imputation data will be analyzed using the same MMRM model as that for the primary analysis, and the results of the analyses will be combined. Imputation will be performed for all available data obtained at each time point between the baseline and Week 4 of the double-blind period.

- (1) Non-monotone missing data will be imputed with an MCMC method.
- (2) Monotone missing data will be imputed with an imputation formula generated using a regression model developed based on the data from the placebo group.

11.1.2 Other assessment variables

11.1.2.1 Change from baseline in the mean NRS score

Summary statistics will be presented. A one-sample t-test will be used for comparisons within each group. For the double-blind period, a two-sample t-test will be used for comparisons between the placebo group and the MR13A9 0.5 µg/kg group. Means and standard deviations will be presented graphically.

The assessment time points are as follows:

- Double-blind period: Weeks 1 to 6
- Entire study period: Weeks 1 to 58, Week 1 of the follow-up period

11.1.2.2 Mean NRS score

Summary statistics will be presented. Means and standard deviations will be presented graphically.

The assessment time points are as follows:

- Double-blind period: Week -1, baseline, Weeks 1 to 6
- Entire study period: Week -1, baseline, Weeks 1 to 58, Week 1 of the follow-up period

11.1.2.3 Percentage of subjects with improvement in the mean NRS score

The number and percentage of subjects with 3-point improvement (change from baseline in the mean NRS score is ≤ -3) and subjects with 4-point improvement (change from baseline in the mean NRS score is ≤ -4) will be presented. For the double-blind period, a Fisher's exact test will be used for comparisons between the placebo group and the MR13A9 0.5 µg/kg group. The percentages of responders will be presented graphically.

The assessment time points are as follows:

- Double-blind period: Weeks 1 to 6
- Entire study period:
 - Table: Weeks 1 to 58, Week 1 of the follow-up period
 - Figure: Weeks 4, 6, 10, 18, 26, 34, 46, and 58

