In the verification part of an overseas phase III clinical study (CR845-CLIN3102), 377 hemodialysis patients with moderate to severe pruritus received MR13A9 0.5 µg/kg or placebo injected into the venous line of the dialysis circuit at the end of each dialysis session 3 times weekly for 12 weeks. The primary endpoint of proportion of subjects with a  $\geq 3$  points improvement in NRS score (Week 12) was 51.0% in the MR13A9 0.5 µg/kg group and 27.6% in the placebo group. MR13A9 0.5 µg/kg group showed significant improvement compared with the placebo group. The incidence of adverse drug reactions was 5.3% (10/188 subjects) in the placebo group and 6.9% (13/188 subjects) in the 0.5 µg/kg group. Common adverse drug reactions (reported in  $\geq 1\%$  of the subjects in the MR13A9 group) included dizziness, somnolence, constipation, headache, hypoesthesia, paraesthesia, and confusional state.

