#### **8.5.3.5 Randomization of subjects**

Based on the treatment assignment table prepared by the person responsible for treatment assignment, the subject registration center will randomly assign subjects eligible for tertiary registration to either the MR13A9 0.5 µg/kg or placebo group at a ratio of 1:1 by a dynamic allocation method using two stratification factors: Prior treatment with nalfurafine hydrochloride notified by the medical institution (for ≥ 2 consecutive weeks in the year prior

---

to the informed consent procedure) and specific signs or symptoms occurring during the screening period ([Appendix 4](#)) confirmed before dialysis on the start day of treatment.

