## 8.6 Sample size

### 8.6.1 Sample size

- Double-blind period

The study will enroll 86 subjects each MR13A9 0.5 µg/kg group and the placebo group (172 in total).

- Extension period

The study will enroll 100 subjects who complete 58-week treatment.

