### 8.6.2 Rationale for the sample size

#### 8.6.2.1 Double-blind period

In a Japanese phase II clinical study (MR13A9-4), the change from baseline in the mean NRS score at Week 4 of the treatment period (mean  $\pm$  standard deviation) was  $-2.15 \pm 1.98$  in the placebo group and  $-3.22 \pm 2.09$  in the MR13A9 0.5 µg/kg group. The difference for the MR13A9 0.5 µg/kg group versus the placebo group at Week 4 of the treatment period was  $-1.04 \pm 0.35$  (adjusted mean  $\pm$  standard error).

For the primary variable of change from baseline in the mean NRS score at Week 4 of the double-blind period, its mean difference for the MR13A9 0.5 µg/kg group versus the placebo group was assumed to be  $-1.0$ , with a common standard deviation of  $2.0$ . Assuming a two-sided significance level of  $5\%$  and a statistical power of  $90\%$ , the sample size required to confirm the superiority of the MR13A9 0.5 µg/kg group to the placebo group using a two-sample t-test was calculated to be 86 subjects per group.

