- All statistical tests will be performed using a two-sided significance level of 5%; however, a two-sided significance level of 15% will be used for the analysis of between-group demographic imbalance.
- Summary statistics to be presented include the number of subjects, mean, standard deviation, minimum, median, maximum, and quartile.
- For the double-blind period, data from the start of the screening period to the end of the double-blind period will be analyzed. Over the entire study period, data from the start of the screening period to the end of the follow-up period will be analyzed.
- Unless otherwise specified, data will be summarized by group and time point for each of the double-blind and entire study periods.

5. Handling of Data

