12.1.1 Incidence of adverse events and adverse drug reactions

The number of events, the number of subjects experiencing events, the incidence of events and its two-sided 95% confidence interval will be presented. For the double-blind period, a Fisher's exact test will be used for comparisons between the placebo group and the MR13A9 0.5 µg/kg group. The difference in the incidence between the placebo group and the MR13A9 0.5 µg/kg groups and its two-sided 95% confidence interval will be presented.

12.1.2 Incidences of adverse events and adverse drug reactions (serious adverse events, adverse events leading to interruption/discontinuation of treatment, and adverse events of special interest)

The events to be tabulated are as follows.

- Double-blind period: Events occurring between the start of study treatment and the end of the double-blind period
- Entire study period
 - Events occurring between the start of study treatment and the end of the follow-up period
 - Events occurring between the start of study treatment and the end of the extension period

The number of events, the number of subjects experiencing events, and the incidence of events will be presented for all events, events leading to death, serious events other than death, events leading to interruption, and events leading to discontinuation.

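### The 3- and 4-point NRS responder comparison uses an unadjusted, conservative Fisher's test and plans no between-group estimate or confidence interval (low severity)

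*SAP*

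**What the plan says.** SAP 11.1.2.3 presents "The number and percentage of subjects with 3-point improvement (change from baseline in the mean NRS score is" at most −3), and likewise for a fall of at least 4 points. For the double-blind period, at Weeks 1 to 6, Fisher's "exact test will be used for comparisons between the placebo group and the" MR13A9 0.5 µg/kg group. Protocol 14.5.3.3 3) says the same. Neither section names a covariate, a between-group difference or ratio, or a confidence interval.

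Three other parts of the plan bear on this:

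- **Adverse events (SAP 12.1.1).** Fisher's test is also used here, but with an estimate: "The difference in the incidence between the placebo group and the" active group is reported with a two-sided 95% CI.
- **Primary model (SAP 11.1.1.1).** The MMRM of NRS change adjusts for baseline mean NRS and prior nalfurafine, and reports an adjusted difference with its CI.
- **Status of the variable (SAP 6.5.2).** Everything except the primary variable is a reference item, without multiplicity adjustment.

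The general rule in SAP section 4 is: "All statistical tests will be performed using a two-sided significance level of 5"%.

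**The concern.** Responder status is a cut of the primary variable, yet its test uses neither of the covariates in the primary model. Baseline also limits who can respond. Entry needs only a mean NRS above 4.0 on a 0 to 10 scale, so a patient starting at 4.1 must average 0.1 or less to be a 4-point responder, while a patient starting at 8 must average 4 or less. Fisher's test is conservative as well, so it rejects less often than its nominal 5% allows.

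The reporting gap is the main issue. A responder rate is a common clinical reading of an NRS result, and the protocol's background section cites one for the overseas phase III study: "The primary endpoint of proportion of subjects with a" 3-point or greater improvement, 51.0% against 27.6% at Week 12. As planned, this trial will give two percentages and a P value, with no between-group effect or precision. That suits a reference item poorly: since it carries no confirmatory claim, the estimate and interval are what a reader needs.

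**Working it through.** **Inputs.** 86 per group (protocol 8.6.1); 1:1 allocation (protocol 8.5.3.5); two-sided 5% (SAP section 4). Phase II Week 4 change (protocol 8.6.2.1): −2.15 (SD 1.98) on placebo, −3.22 (SD 2.09) on 0.5 µg/kg. Planning values (same section): difference −1.0, SD 2.0. Overseas rates (protocol 1.3.2.2): 27.6% and 51.0%.

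**1. The plan's own figure.** The noncentrality is 1.0 / (2.0 × √(2/86)) = 3.28. The two-sample t-test then has power 0.9032 at 86 per group and 0.8999 at 85, so 86 is reproduced. It sizes the primary variable; the documents give no power for the responder test.

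**2. Implied Week 4 responder rates,** assuming normal changes, Φ((cut − mean)/SD):

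- 3-point: placebo Φ((−3 + 2.15)/1.98) = 33.4%; active Φ((−3 + 3.22)/2.09) = 54.2%.
- 4-point: placebo Φ((−4 + 2.15)/1.98) = 17.5%; active Φ((−4 + 3.22)/2.09) = 35.4%.
- Planning values, with means −2.15 and −2.15 − 1.0 = −3.15 and SD 2.0: 33.5% vs 53.0% (3-point) and 17.8% vs 33.5% (4-point).

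**3. True size of Fisher's test.** With a common rate p, size = Σ b(x; 86, p) b(y; 86, p) over all pairs (x, y) with Fisher P ≤ 0.05, where b is the binomial probability.

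| Common rate | True size | Share of 0.05 |
|---|---|---|
| 7.5% | 0.0253 | 51% |
| 17.5% | 0.0309 | 62% |
| 27.6% | 0.0334 | 67% |
| 33.4% | 0.0341 | 68% |
| 50% | 0.0392 | 78% |

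For common rates of 15% to 60% the range is 0.031 to 0.039. With an assumed 5% or 10% loss (82 or 77 per arm) it is 0.030 to 0.036.

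**4. Power at 86 per arm.** Fisher and Pearson chi-square are by exact enumeration. The adjusted column is a simulated likelihood ratio test from logistic regression on treatment, baseline and prior nalfurafine. It assumes a normal baseline, prior nalfurafine in half the patients with no prognostic effect, and the baseline-change correlation shown (higher baseline, larger fall). There were 12,000 runs for the phase II rates and 8,000 for the planning rates; Monte Carlo error is about 0.3 to 0.5 points.

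| Rates, placebo vs active | Fisher | Chi-square | Loss | Adjusted, correlation 0 / 0.3 / 0.5 |
|---|---|---|---|---|
| 3-point, phase II | 75.6% | 80.2% | 4.6 | 79.4 / 81.1 / 85.8% |
| 4-point, phase II | 71.2% | 77.2% | 6.0 | 77.4 / 79.4 / 84.0% |
| 3-point, planning | 69.5% | 74.7% | 5.2 | 73.8 / 75.9 / 81.0% |
| 4-point, planning | 59.9% | 67.0% | 7.1 | 67.2 / 69.4 / 73.9% |
| Overseas 27.6% vs 51.0% | 85.8% | 89.0% | 3.2 | not run |

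Fisher's test therefore costs 3.2 to 7.1 points against chi-square. Against the adjusted model the total runs from 79.4 − 75.6 = 3.8 to 73.9 − 59.9 = 14.0 points. At zero correlation the adjusted model does no better than chi-square; at 0.5 it adds a further 5.6 points (85.8 − 80.2) to 6.9 points (73.9 − 67.0). Under the null, its simulated size was about 0.05 to 0.06, so a small part of its gain is a slightly high error rate.

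**5. The interval the plan leaves out,** d ± 1.96 √(p₁(1 − p₁)/86 + p₂(1 − p₂)/86), at the phase II rates:

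- 3-point: 20.8 ± 1.96 × 7.40 = 6.3 to 35.3 points.
- 4-point: 17.9 ± 1.96 × 6.59 = 5.0 to 30.9 points.

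**The case against.** The case for leaving the plan alone is fair in several respects.

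- **No decision depends on it.** The responder rate is neither the primary variable nor a listed secondary endpoint, and it was never powered. A conservative test cannot create a false claim. This stands and keeps the severity low.
- **Baseline is not ignored.** SAP 11.3 repeats the responder analysis by baseline NRS (below 6, 6 or more) and by prior nalfurafine. This stands in part: subgroup tables show whether results vary, but give no overall adjusted estimate or interval.
- **A crude difference can be worked out** from the reported percentages. True, and the missing item is properly called a between-group estimate. An adjusted one cannot be recovered from those percentages.
- **The gain from adjustment is assumed.** It depends on a correlation the documents do not give. This stands; only the loss against chi-square is free of that assumption.
- **The overseas rates are for Week 12,** whereas the primary time point here is Week 4. True, so the comparison between studies is loose.

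A reader might also infer that the test runs at about half its nominal level. The documents do not support that: half needs a common responder rate near 7.5%, well below the implied Week 4 placebo rates. Such a rate might occur in early weeks, but no early-week rates are given. Nor does the floor at zero bias the crude comparison, since randomisation balances baseline in expectation.

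**Conclusion.** The concern holds as a low-severity improvement. The firm part needs no assumption: SAP 11.1.2.3 and protocol 14.5.3.3 3) plan a test without a between-group effect or interval and without the primary model's covariates, and no reason is given for departing from the practice in SAP 12.1.1.

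The numerical part is modest. Size is roughly 60% to 70% of nominal at the implied Week 4 placebo rates; the loss is about 3 to 7 power points to Fisher's test itself, and about 4 to 14 in total against an adjusted model. These figures assume normal changes, 86 evaluable patients per arm and, for the last range, correlations of 0 to 0.5. It would be wrong to conclude that type I error is inflated or that the superiority conclusion is in doubt: that conclusion comes from the adjusted MMRM.

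**What to change.** In SAP 11.1.2.3, for the double-blind period:

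1. Report the between-group difference in responder percentages with a two-sided 95% CI at each week, mirroring SAP 12.1.1. This alone closes the reporting gap.
2. Make the main comparison, at least at Week 4, a logistic regression on treatment, baseline mean NRS and prior nalfurafine. Report the odds ratio and the standardised risk difference, each with a 95% CI, and name the CI method for the latter.
3. Within the prior-nalfurafine subgroups, drop that covariate, as SAP 11.3 already does for the primary model.
4. Keep Fisher's test as supportive, and as the stated fallback where responders are too few for the model.

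No new data are needed and the primary analysis is unchanged. The cost is SAP wording and up to 2 thresholds × 6 weeks = 12 models, plus up to 12 × 4 = 48 if all are repeated in the four subgroups. Separation is possible in early weeks, hence the fallback. Restricting the model to Week 4 cuts the overall count to two. If the double-blind data have already been unblinded, label the addition as made afterwards.

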11.1.2.4 Change from baseline in the daily NRS score

The same analysis as described in “[11.1.1.1 Primary analysis](#)” will be performed using the data obtained from Days 2 to 15 of the double-blind period. The analysis will include all available data obtained at each time point from Days 2 to 15 of the double-blind period as objective variables.

The assessment time points are as follows:

- Double-blind period: Days 2 to 15

11.1.2.5 Daily NRS score

Summary statistics will be presented. Means and standard deviations will be presented graphically.

The assessment time points are as follows:

- Double-blind period: Days –6 to 15

11.2 Secondary Endpoints

11.2.1 Itch score based on the Shiratori's severity criteria

Higher of daytime or night-time score, daytime score, and night-time score will be analyzed. The mean itch score and the change from baseline at each time point and the change from baseline in daily itch score will be calculated using the same calculation formulas as those for the mean NRS score, change from baseline in NRS score, and change from baseline in daily NRS score as described in “[11.1 Primary Endpoint](#).”

11.2.1.1 Change from baseline in the mean itch score

The same analysis as “[11.1.1.1 Primary analysis](#)” will be performed. However, the covariate of the model will be the baseline of the data to be analyzed.

The same analysis as “[11.1.2.1 Change from baseline in the mean NRS score](#)” will be performed.

The assessment time points are as follows:

- Analysis using a model: Weeks 1 to 4
- Other
 - Double-blind period: Weeks 1 to 6
 - Entire study period: Weeks 1 to 58, Week 1 of the follow-up period

11.2.1.2 Mean itch score

The same analysis as “[11.1.2.2 Mean NRS score](#)” will be performed.

The assessment time points are as follows:

- Double-blind period: Week –1, baseline, Weeks 1 to 6
- Entire study period: Week –1, baseline, Weeks 1 to 58, Week 1 of the follow-up period

11.2.1.3 Change from baseline in daily itch score

The same analysis as “[11.1.2.4 Change from baseline in the daily NRS score](#)” will be performed.

However, the covariate of the model will be the baseline of the data to be analyzed.

The assessment time points are as follows:

- Double-blind period: Days 2 to 15

11.2.1.4 Daily itch score

The same analysis as “[11.1.2.5 Daily NRS score](#)” will be performed.

The assessment time points are as follows:

- Double-blind period: Days –6 to 15

11.2.1.5 Percentage of subjects with improvement in night-time mean itch score

Night-time mean itch score will be analyzed.

For the subjects with a baseline mean itch score of 3 or more, the number and percentage of subjects with improvement (the mean itch score is ≤ 2) will be presented. For the double-blind period, a Fisher's exact test will be used for comparisons between the placebo group and the MR13A9 0.5 $\mu\text{g}/\text{kg}$ group. The percentages of responders will be presented graphically.

The assessment time points are as follows:

- Double-blind period: Weeks 1 to 6
- Entire study period:
 - Table: Weeks 1 to 58, Week 1 of the follow-up period
 - Figure: Weeks 4, 6, 10, 18, 26, 34, 46, and 58

11.2.2 Skindex-16

The overall score and subscores (symptoms score, emotions score, and functioning score) will be analyzed.

11.2.2.1 Changes from baseline in Skindex-16

Analysis of covariance with treatment group as a fixed effect and the baseline score as a covariate will be performed on the data obtained at the end of the double-blind period. The number of subjects and adjusted mean change for each group, with standard error and two-sided 95% confidence interval, will be presented. The adjusted mean between-group difference in the change for the placebo group and the MR13A9 0.5 $\mu\text{g}/\text{kg}$ groups, with standard error and two-sided 95% confidence interval, as well as the P value will be presented.

The same analysis as “[11.1.2.1 Change from baseline in the mean NRS score](#)” will be performed. The assessment time points are as follows:

- Analysis of covariance: At the end of the double-blind period
- Other
 - Double-blind period: Week 4, at the end the double-blind period
 - Entire study period: Weeks 4, 10, 18, 26, 34, 46, and 58

11.2.2.2 Skindex-16

The same analysis as “[11.1.2.2 Mean NRS score](#)” will be performed.

The assessment time points are as follows:

- Double-blind period: Baseline, Week 4, at the end the double-blind period
- Entire study period: Baseline, Weeks 4, 10, 18, 26, 34, 46, and 58

11.2.3 5-D Itch Scale

The overall score and component scores (duration, degree, direction, disability, and distribution scores) will be analyzed.

11.2.3.1 Changes from baseline in 5-D itch scale

The same analysis as “[11.2.2.1 Changes from baseline in Skindex-16](#)” will be performed.

The assessment time points are as follows:

- Analysis of covariance: At the end of the double-blind period
- Other
 - Double-blind period: Week 4, at the end the double-blind period
 - Entire study period: Weeks 4, 10, 18, 26, 34, 46, and 58

11.2.3.2 5-D Itch Scale

The same analysis as “[11.1.2.2 Mean NRS score](#)” will be performed.

The assessment time points are as follows:

- Double-blind period: Baseline, Week 4, at the end the double-blind period
- Entire study period: Baseline, Weeks 4, 10, 18, 26, 34, 46, and 58

11.2.4 PGIC

The number and percentage of subjects with global symptoms will be presented. For the double-blind period, a two-sample Wilcoxon test will be used for comparisons between the placebo group and the MR13A9 0.5 µg/kg group. The percentage of global symptoms will be presented graphically.

The assessment time points are as follows:

- Double-blind period: Week 4, at the end the double-blind period
- Entire study period: Weeks 4, 10, 18, 26, 34, 46, and 58

11.3 Efficacy Subgroups

The same analyses as described in “[11.1.1.1 Primary analysis](#)” and “[11.1.2 Other assessment variables](#)” will be performed on data from the double-blind period in each of the subgroups defined by prior treatment with nalfurafine hydrochloride (no, yes) and mean NRS score at baseline (< 6, ≥ 6). For the subgroup defined by prior treatment with nalfurafine hydrochloride, only the mean NRS score at baseline will be used as a covariate in the model.

12. Safety

